14.6 Safety Analysis

Safety evaluations will be presented by escalating dose and based on the incidence, intensity and type of adverse events (AEs).

All AEs occurring on study will be listed in by-participant data listings. A by-dose tabulation will be provided that enumerates AEs by maximum severity. Deaths, SAEs and events resulting in study discontinuation will be tabulated.

14.7 Efficacy Analyses

Primary and secondary analyses will be performed in both the FAS and PPS populations and will include calculating the proportion of patients having an overall response (MR or better) and major response (CR or VG). Confidence intervals (95%) about these point estimates will be presented. Time to progression (TTP) and time to next therapy (TNT) as defined in sections 10.4, and 10.5, respectively will be estimated using Kaplan and Meier methodology with median time plus 25th and 75th percentile time to progression free survival along with 95% confidence intervals being provided, as appropriate. In addition, landmark analysis for 2 and 4 year progression free survival will be performed.

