1. OBJECTIVES

1.1 Study Design

This is a single-arm, open-label, prospective phase II study to evaluate the safety and efficacy of IDR in symptomatic untreated WM patients. The study treatment will consist on an induction and a maintenance phase. Dose modification will be permitted for toxicity.

IDR Induction:

Cycles 1 and 2 will consist on ixazomib 4 mg and dexamethasone 20 mg IV or PO administered on days 1, 8 and 15.

Cycles 3-6 will consist on ixazomib 4 mg PO and dexamethasone 20 mg IV or PO on days 1, 8 and 15, and rituximab 375 mg/m² IV on day 1 every 28 days.

Total duration of induction: 24 weeks.

IDR Maintenance:

Maintenance therapy will start 2 months ± 2 weeks after day 1 of cycle 6 and will consist on ixazomib 4 mg PO and dexamethasone 20 mg IV or PO administered on days 1, 8 and 15, and and rituximab 375 mg/m² IV administered on day 1 every 2 months for 1 year (6 cycles).

Total duration of maintenance: 52 weeks.

Supportive therapy:

Acyclovir 400 mg PO BID or Valacyclovir 1000mg PO QD will start on day 1 of study and will continue for 6 months after the last dose of ixazomib.

Famotidine 20 mg PO (or other gastritis prophylactic medication) will start on day 1 of study and will continue until the last dose of dexamethasone.

Acetaminophen 650 mg PO, diphenhydramine 50 mg PO and famotidine 20mg IV will be administered at least 30 minutes prior to each rituximab infusion.

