9. STUDY CALENDAR

	Screening ≤30 days from study entry	Induction Phase q28 days +/- 3 Days*,**						Inter-phase Visit Within 4 weeks +/- 2 weeks of completion of Cycle 6 of induction	Maintenance Phase (Beginning 8 weeks +/- 2 weeks after Induction C6D1) q 8 weeks +/- 2 weeks			Off Treatment Visit within 4 weeks +/- 2 weeks of completion of all treatment or removal from trial	Follow-up Q6 months +/- 2 weeks for 2 years ⁶
		Cycles 1 and 2			Cycles 3-6				Cycles 1-6				
		D1	D8	D15	D1	D8 ⁸	D15 ⁸		D1**	D8	D15		
Dexamethasone		X	X	X	X	X	X		X	X	X		
Ixazomib		X	X	X	X	X	X		X	X	X		
Rituximab					X				X				
Informed consent	X												
Physical exam (Ht, Wt, BSA, VS)	X	X			X			X	X			X	X
History	X	X						X	X			X	X
Concurrent meds	X	X			X			X	X			X	X
ECOG Performance Status	X	X			X			X	X			X	X
CBC w/diff, platelets	X	X	X	X	X	X	X	X	X			X	X
Serum chemistry ¹	X	X	X	X	X	X	X	X	X ¹			X	X
Coagulation Profile (PT, PTT, INR)	X												
Quantitative IgM, IgA, IgG SPEP and immunofixation ²	X	X			X			X	X			X	X
Beta-2-Microglobulin	X												
B-HCG ³	X												
Hepatitis B and C Screening	X												
MYD88 L265P status bone marrow (PCR)	X							X				X	
MYD88 L265P status peripheral blood (qPCR)	X ⁷												
CXCR4 mutational status (Sanger)	X												
Adverse event evaluation	X	X			X			X	X			X	
Neuropathy Assessment	X	X			X			X	X			X	
CT scan w/ contrast Chest/Abdomen/Pelvis ⁵	X ⁴							X ⁵				X ⁵	
Bone Marrow Biopsy and Aspiration ²	X ⁴							X				X	

*: Peripheral Neuropathy questionnaire and labs do not need to be repeated if Day 1 of induction treatment within 10 days of screening. If labs are repeated on C1D1 they must be reviewed prior to study drug administration and meet eligibility.
 **: For criteria for administration of treatment see Section 6.2
 1: Comprehensive chemistry panel: Albumin, total bilirubin, BUN, creatinine, calcium, chloride, glucose, potassium, total protein, sodium, SGOT, SGPT, alkaline phosphatase, magnesium
 2: Bone Marrow Biopsy and Aspiration will be required at Screening, Interphase visit, and Off-Treatment Visit. May be Repeated at other time points to confirm a suspected complete remission and at the Principal Investigator's discretion
 3: Serum pregnancy test for women of childbearing potential
 4: If done within 90 days of screening, this will not be required at the screening visit

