 5: Repeat to assess disease response or confirm a suspected complete remission if participant had lymphadenopathy, hepatosplenomegaly, or an extramedullary mass at baseline defined as adenopathy >1.5 cm in any axis, and splenomegaly >15 cm in the craniocaudal axis.
 6. Follow-up visits will be required every 6 months +/- 2 weeks after EOT visit. 3 month follow-up visits are recommended.
 7. MYD88 L265P mutational status by qPCR at screening and, if mutant, subsequently every 3 months while on therap.
 8. Safety Laboratories do not need to be performed on Day 8 and 15 of Induction Cycles 4-6, or any Maintenance cycles.

CONFIDENTIAL

This document is confidential. Do not disclose or use except as authorized.

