10.4 Time to Progression

Time to Progression (TTP) is defined as the duration of time from start of treatment to time of disease progression as defined in section 10.1. Death from any cause or initiation of a new anti-neoplastic therapy will also be considered a progression event.

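### For patients who complete treatment, the first required 6-month follow-up visit falls around the 2-year PFS landmark (nominally week 96 to 111, against week 104.4), so the 2-year estimate depends on visit timing and can be biased upward

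*Combined protocol and SAP*

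**What the plan says.** Section 14.7 plans the landmark: "In addition, landmark analysis for 2 and 4 year progression free survival will be performed". PFS itself is not defined. The nearest definition is TTP in section 10.4, the "duration of time from start of treatment to time of disease progression", with death and new anti-neoplastic therapy also counted as events.

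The visit dates come from four places:

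- Section 1.1: "Total duration of induction: 24 weeks"; "Maintenance therapy will start 2 months ± 2 weeks after day 1 of cycle 6"; "Total duration of maintenance: 52 weeks", in six cycles given every 2 months.
- Section 9, calendar header: "Maintenance Phase (Beginning 8 weeks +/- 2 weeks after Induction C6D1) q 8 weeks +/- 2 weeks".
- Section 9, end of treatment: "Off Treatment Visit within 4 weeks +/- 2 weeks of completion of all treatment or removal from trial". The quantitative IgM row is read as marked at this visit and at the follow-up visits.
- Section 9, footnote 6: "Follow-up visits will be required every 6 months +/- 2 weeks after EOT visit", with 3-month visits recommended.

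Section 5.5 gives the same 6-month interval, with 3 months preferred, but counts it from removal from study rather than from the Off Treatment Visit. Section 10.1 defines progression by a rise in IgM from its lowest value, with a repeat test 2 ± 1 weeks later when IgM is the reason for suspicion, or by progression of disease-related symptoms. No section says how a progression found between visits is dated.

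**The concern.** A progression defined by IgM cannot be recorded until IgM is measured. If the last required measurement before the landmark is at the Off Treatment Visit, and the next is just after the landmark, an IgM-only progression arising between them is dated after 2 years. The 2-year figure then reflects status some 24 weeks earlier, and the error runs only upward. The issue is where one visit sits relative to the landmark, not how long follow-up lasts. It affects a promised secondary estimate in a single-arm trial; the primary VGPR endpoint is not touched.

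**Working it through.** **Landmark.** 2 × 365.25 / 7 = 104.4 weeks from C1D1.

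**Plan's own durations.** 24 + 52 = 76 weeks. The calendar reproduces this total: induction C6D1 is week 20, maintenance starts at 20 + 8 = 28, and six 8-week cycles end at 28 + 48 = 76. The totals agree because the 4 weeks between the end of induction (24) and the start of maintenance (28) offset 52 − 48 = 4.

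**First required follow-up, end-of-cycle reading.** Off Treatment Visit at 76 + 4 = 80. Six months is 26.1 weeks, so the visit is at 80 + 26.1 = 106.1, which is 1.7 weeks after the landmark. The gap from the Off Treatment Visit to the landmark is 104.4 − 80 = 24.4 weeks.

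**Other readings.** Treatment completion may mean the last dose (day 15 of maintenance cycle 6) or the end of cycle 6. Cycles may be 8 weeks (calendar) or 2 months (section 1.1; six make 52.2 weeks). Removal from study in section 5.5 is taken here as the end of treatment.

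| Cycles | Completion means | End of treatment | Off Treatment Visit | Follow-up, footnote 6 anchor | Follow-up, section 5.5 anchor |
|---|---|---|---|---|---|
| 8 weeks | last dose | 70 | 74 | 100.1 | 96.1 |
| 8 weeks | end of cycle 6 | 76 | 80 | 106.1 | 102.1 |
| 2 months | last dose | 74.2 | 78.2 | 104.3 | 100.3 |
| 2 months | end of cycle 6 | 80.9 | 84.9 | 111.0 | 107.0 |

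The nominal date thus runs from week 96.1 to week 111.0. On the week-106.1 reading, the ± 2-week windows on the Off Treatment Visit and the follow-up visit alone span 102.1 to 110.1.

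**Size of the bias.** Assume exponential PFS with median m, all cycles completed, progression found only at scheduled visits and dated at detection. Then S(t) = 0.5^(t/m), and the bias is S(last assessment before the landmark) − S(104.4). The medians of 24 and 36 months are illustrative; 56 months takes the projection that section 2.3 gives as a lower bound for the bortezomib triplet.

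| Median | True 2-year PFS | S(80) | Bias, last look at week 80 | Week 100.1 | Week 102.1 |
|---|---|---|---|---|---|
| 24 months | 0.500 | 0.588 | +8.8 points | +1.4 | +0.8 |
| 36 months | 0.630 | 0.702 | +7.2 | +1.2 | +0.6 |
| 56 months | 0.743 | 0.796 | +5.3 | +0.9 | +0.5 |

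**Visit windows.** On the end-of-cycle reading, with dates spread over the allowed windows, about 70% of completers have their first follow-up after week 104.4. The simulated bias is about +6, +5 and +3 to +4 points. On the last-dose reading with drift it is about +1 to +3.

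**Delays.** Section 6.2.1 allows cycle delays in 1-week steps up to 28 days, or longer at the investigator's discretion. On the last-dose reading the margin is 104.4 − 100.1 = 4.3 weeks over 12 cycles. A cumulative 5-week delay puts the Off Treatment Visit at 79 and follow-up at 105.1, and the bias returns to about +9, +7 and +6.

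**The case against.** The strongest reply is that the order of visit and landmark is not fixed. On the 8-week calendar, three of four readings put the visit before week 104.4, and the wording gives the last-dose reading some support: the Inter-phase Visit is tied to the end of a named cycle, whereas the Off Treatment Visit is tied to the end of treatment. This stands, and it is why the point is stated as a range. It does not remove the problem, because the margin is a few weeks at most and allowed delays can use it up.

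Several stronger readings are tempting and are not supported:

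- **That week 106 is the first off-treatment assessment.** It is not. The Off Treatment Visit comes first and includes IgM, so a progression between the end of treatment and that visit can be found there. The unobserved stretch starts at that visit.
- **That the analysis will necessarily report week-80 PFS as 2-year PFS.** Symptomatic progression, death and new therapy need not wait for a scheduled visit. With the recommended 3-month visits, an assessment falls at about week 87 to 98 on the footnote 6 anchor, before the landmark in each case. Section 14.7 names Kaplan-Meier for TTP and time to next therapy, and dating at detection is an assumption. Patients who stop early follow another timetable.
- **That the trial is biased against the bortezomib triplet.** No comparison is planned, section 2.3 cites a projected duration rather than a 2-year rate, and that study's visit schedule is not given.

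The bias is also modest beside sampling error: at 74.3% with 26 patients, √(0.743 × 0.257 / 26) is about 9 points. That limits its importance, but sampling error is not one-directional and this error is.

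The final analysis is set for when all patients have completed maintenance (section 1.1), about week 76 for the last one, before that patient reaches 2 years. Required follow-up also ends before 4 years. Both are separate matters, which moving this visit would not resolve.

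**Conclusion.** The concern holds in a limited form. For on-schedule completers, the documents leave the first required follow-up visit anywhere from about week 96 to week 111, and on the calendar's end-of-cycle reading it falls just after the 2-year landmark. The 2-year PFS estimate is therefore sensitive to visit timing and to an unstated dating rule, with any error upward. The figures of about +9, +7 and +5 points are upper values: they require nominal timing, no optional visits and IgM-only progression dated at detection. Allowing for windows gives about +6, +5 and +3 to +4. A visit at about week 100 to 102 gives about +0.5 to +3. All rest on exponential PFS and assumed medians. This is worth correcting because it is cheap, but it bears on a secondary descriptive estimate only.

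**What to change.** 1. **Footnote 6 and section 5.5.** Reconcile the anchor for follow-up, and state whether treatment completion means the last dose or the end of cycle 6.
2. **Footnote 6, completers without progression.** Time the first required follow-up assessment (IgM and symptoms) from C1D1 so that it falls at or just before week 104, for example week 102 ± 2. Patients who stop early keep 6-monthly visits from their own Off Treatment Visit; the C1D1 anchor must not delay their reassessment.
3. **Section 14.7.** Add a supplementary 2-year PFS estimate that treats progression as interval-censored between the last negative and first positive assessment. State whether the first qualifying IgM value or its confirming repeat dates the event, since the repeat may fall after the landmark.

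With a visit at week 102, the residual bias under the same assumptions is below 1 point at each of the three medians.

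**Cost.** No visit is added. One existing visit shifts: about 4 weeks earlier on the week-106.1 reading, or about 2 weeks later on the week-100.1 reading, where 102 − 74 = 28 weeks still fits 6 months + 2 weeks (28.1). There is slightly more analysis work, and the reported 2-year PFS may be a few points less favourable.

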A Screening visit will be conducted within 30 days before baseline (baseline being Day 1, Cycle 1, before study drug administration). At this visit, a medical history will be obtained with complete physical examination, vital signs, and an ECOG performance status. A bone marrow aspirate and biopsy, beta-2-microglobulin, serum and protein electrophoresis with quantification of immunoglobulins (IgM, IgG, IgA) and immunofixation studies, and computed tomography (CT) scans of the chest, abdomen and pelvis will also be conducted at the Screening visit. Bone marrow biopsy and CT scans will not be required if collected up to 90 days prior to screening visit. MYD88 L265P mutational status will be determined by BWH Molecular Diagnostics Lab. CXCR4 mutational status and FcγRIIIA-158 polymorphisms will be determined by the Bing Center for Waldenström Macroglobulinemia Laboratory. Clinical laboratory tests including a complete blood count plus differential, electrolytes, BUN, creatinine, comprehensive chemistry panel, magnesium, total bilirubin, liver function tests, and serum pregnancy tests for women of child-bearing potential will also be performed at the Screening visit.

Patients who meet the eligibility requirements at the Screening visit, and provide written consent, will be enrolled in the study and initiated on study treatment. Patients will be evaluated for

CONFIDENTIAL

This document is confidential. Do not disclose or use except as authorized.

tolerance and response on Day 1 of each cycle for the duration of the trial. Patients will be eligible to continue therapy as long as they do not demonstrate progressive disease or unacceptable toxicity. Modified response criteria updated at the Sixth International Workshop on WM (Owen 2013) will be used to assess response, stable disease, and progressive disease. Response outcomes to be determined will include: ORR and major response rates (including VGPR and CR rates); landmark analysis for 2 and 4-year PFS; median TTP; median TTNT. The final analysis will be undertaken when all participants would have completed the maintenance phase of the study.

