4.2 Registration Process for DF/HCC and DF/PCC Institutions

5. TREATMENT PLAN

Treatment will be administered on an outpatient or inpatient basis. Expected toxicities and potential risks as well as dose modifications for ixazomib, rituximab, and dexamethasone are described in Section 6 (Expected Toxicities and Dosing Delays/Dose Modification). No investigational or commercial agents or therapies other than those described below may be administered with the intent to treat the participant’s malignancy.

IDR Induction Phase					
Agent	Premedications	Dose	Route	Schedule	Cycle Length
Dexamethasone	None	20 mg	IV or PO	Days 1, 8, 15 Before ixazomib and rituximab	Every 4 weeks for Cycles 1-6 Rituximab omitted from cycles 1 and 2
Ixazomib	None	4 mg	PO	Days 1, 8 15 After dexamethasone	
Rituximab	Diphenhydramine 25-50 mg PO/IV Acetaminophen 650-1000 mg PO Famotidine 20mg IV	375 mg/m ²	IV infusion	Day 1 After Ixazomib	

IDR Maintenance Phase					
Agent	Premedications	Dose	Route	Schedule	Cycle Length

CONFIDENTIAL

This document is confidential. Do not disclose or use except as authorized.

Dexamethasone	None	20 mg	IV or PO	Day 1, 8, and 15 Before Ixazomib and Rituximab	Every 8 weeks +/- 2 weeks for Cycles 1-6
Ixazomib	None	4 mg	PO	Day 1, 8, and 15 After Dexamethasone	
Rituximab	Diphenhydramine 25-50 mg PO/IV Acetaminophen 650-1000 mg PO Famotidine 20mg IV	375 mg/m ²	IV infusion	Day 1 After Ixazomib	

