5.5 Duration of Follow Up

CONFIDENTIAL

This document is confidential. Do not disclose or use except as authorized.

Participants will be followed every six months (every 3 months preferred) for two years after removal from study until next therapy or until death. Participants removed from study for unacceptable adverse events will be followed until resolution or stabilization of the adverse event.

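### The 4-year PFS landmark is not supported by the planned follow-up schedule or by the only stated analysis time

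*Combined protocol and SAP*

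**What the plan says.** The 4-year result is promised twice, without conditions. Section 14.7 states that "landmark analysis for 2 and 4 year progression free survival will be performed", and Section 1.1 includes "landmark analysis for 2 and 4-year PFS" among the outcomes to be determined.

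One analysis time is given, in Section 1.1: "The final analysis will be undertaken when all participants would have completed the maintenance phase of the study". No later cut for time-to-event endpoints is named.

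The length of maintenance appears in two forms: "Total duration of maintenance: 52 weeks" in Section 1.1, and "Every 8 weeks +/- 2 weeks for Cycles 1-6" in the Section 5 table, which is 48 weeks nominally.

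Follow-up after treatment is described in Section 5.5: "Participants will be followed every six months (every 3 months preferred) for two years after removal from study until next therapy or until death". The Section 9 calendar heads its last column "Follow-up Q6 months +/- 2 weeks for 2 years", and its footnote 6 sets the anchor: "Follow-up visits will be required every 6 months +/- 2 weeks after EOT visit".

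PFS has no definition of its own. Section 10.4 measures TTP from the start of treatment and counts death and new therapy as events, so treatment start is taken here as the PFS origin.

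**The concern.** A PFS probability at 4 years needs patients who are still under progression assessment at 4 years. Kaplan-Meier gives no estimate beyond the last follow-up time unless the curve has already reached zero. That is unlikely here: Section 2.3 cites a projected PFS above 56 months for the earlier bortezomib, dexamethasone and rituximab regimen. If a comparable patient group had exponential PFS with a median of 56 months (an assumption, for scale only), about 0.5^(48/56) = 55% would still be progression-free at 48 months.

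If both the schedule and the data cut fall short of 4 years, the sponsor must either report the landmark as not estimable or rest it on a few patients whose treatment happened to run late. Either way a committed result is not delivered as planned.

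**Working it through.** **Units.** 1 year = 52.18 weeks and 1 month = 4.348 weeks. So 2 years = 104.4 weeks, 3 years = 156.5 and 4 years = 208.7.

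**The plan's own durations.** Induction is 6 × 4 = 24 weeks, as Section 1.1 states. Six cycles of 2 calendar months give 6 × 2 × 4.348 = 52.2 weeks, which reproduces the 52 weeks in Section 1.1. Six cycles of 8 weeks (Sections 5 and 9) give 48. Both are carried forward.

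**1. End of scheduled progression follow-up, nominal.** Day 1 of induction cycle 6 is week 20. Maintenance starts 8 weeks later, at week 28. Then add maintenance, 4 weeks to the off-treatment visit, and 2 years:

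- 48-week maintenance: 20 + 8 + 48 + 4 + 104.4 = **184.4 weeks** (42.4 months), about 24 weeks short of 208.7.
- 52-week maintenance: 20 + 8 + 52 + 4 + 104.4 = **188.4 weeks** (43.3 months), about 20 weeks short.

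**2. Patients who stop early without progression.** Stopping at week x gives x + 4 + 104.4 = x + 108.4. For x = 24 (end of induction) this is **132.4 weeks**, about 76 weeks short.

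**3. Most favourable windows.** Each of the five induction intervals runs 3 days late (15/7 = 2.14 weeks). Maintenance start and every maintenance cycle run 2 weeks late, the off-treatment visit falls at 6 weeks, and the last follow-up visit is 2 weeks late:

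- 8-week cycles: 20 + 2.14 + 10 + 60 + 6 + 106.4 = 204.5 weeks, still 4.2 short.
- Calendar 2-month cycles (8.70 + 2 = 10.70 weeks each): 20 + 2.14 + 10.70 + 6 × 10.70 + 6 + 106.4 = **209.4 weeks**, just past 4 years.

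**4. Follow-up at the stated cut.** The first patient's potential follow-up equals accrual time plus time to the end of maintenance. Maintenance ends at week 76 (17.5 months) or week 80 (18.4 months). Section 14.8 expects accrual over 12 to 15 months:

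- Shortest: 12 + 17.5 = **29.5 months**.
- Longest: 15 + 18.4 = **33.4 months**.

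For sensitivity, accrual time can be taken from the two sample sizes in Sections 14.1 and 14.8 at 2 to 3 patients per month. It then runs from 26/3 = 8.7 to 33/2 = 16.5 months, and the first patient has 26.1 to 34.9 months. For even one patient to have 48 months on the nominal schedule, accrual would have to last 48 − 18.4 = 29.6 to 48 − 17.5 = 30.5 months, about twice the upper expectation.

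**5. The 2-year landmark.** In step 2, x + 108.4 always exceeds 104.4, so 2 years lies inside scheduled follow-up even for early stoppers. At the stated cut, patients enrolled in the last 5.6 to 6.5 months (24 − 18.4 and 24 − 17.5) would be censored before 24 months. With n = 26, uniform accrual over 12 to 15 months and the same exponential assumption, the Greenwood standard error of 2-year PFS rises from 0.086 with complete follow-up to between 0.089 and 0.091.

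**The case against.** The best counter-argument is that the schedule does not make 4 years impossible. This stands. With calendar 2-month cycles and every window at its latest, follow-up reaches 209.4 weeks. Section 6.2.1 also allows cycle delays of up to 28 days, or longer at the investigator's discretion, so roughly 20 to 24 weeks of accumulated delay would carry a patient to 4 years. A reader might infer from the nominal shortfall that no patient can ever be observed at 4 years; the documents do not support that. What they also lack is any basis for expecting enough such patients to form a usable risk set.

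The data-cut result depends on an accrual expectation. Section 14.1 reports that 27 patients were accrued but not how long it took, and treatment delays would also move the cut. That no patient has 48 months at the cut is therefore an expectation under the stated accrual, not a certainty.

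Section 5.5 is loosely worded, and its references to next therapy and death could be read as open-ended follow-up. The calendar heading and footnote 6 point to 2 years after the off-treatment visit. The texts should be reconciled, but as they stand they do not establish follow-up beyond 2 years. The three-year duty in Section 11.2 concerns new primary malignancies and schedules no progression assessment.

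Finally, this is one descriptive summary with no hypothesis attached, and Kaplan-Meier output would simply show it as not estimable. That is fair and limits the weight of the point.

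**Conclusion.** The concern holds in a limited form. Followed as written, the plan is not expected to give a usable 4-year PFS estimate. Nominal progression follow-up ends 20 to 24 weeks too early for patients who complete treatment, and about 76 weeks too early for a non-progressor who stops at week 24. At the only stated cut, the longest potential follow-up is about 29.5 to 33.4 months. Either limit alone is enough on the nominal schedule, so a later cut by itself does not rescue the landmark.

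This rests on treatment start as the time origin, the calendar's 2-year limit, the nominal visit schedule and the expected 12 to 15 month accrual. The conclusion is the same with 48-week or 52-week maintenance.

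A reader might infer that the efficacy conclusions as a whole are in doubt. They are not. The VGPR endpoint, the success rule and the safety analysis do not use this follow-up, and 2-year PFS remains estimable with a small loss of precision at the stated cut.

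**What to change.** - Keep the response analysis at completion of maintenance. State in Sections 1.1 and 14.7 that PFS, TTP and TNT are analysed when the 2-year post-treatment follow-up is complete.
- Reconcile Section 5.5 with the Section 9 calendar and footnote 6 on the length and starting point of follow-up. Reconcile the 48-week and 52-week maintenance durations too.
- Remove the 4-year landmark from Sections 1.1 and 14.7 by a documented amendment. A 3-year landmark (156.5 weeks) is an optional replacement. It is estimable only at the later cut, because 33.4 months is below 36, and non-progressors who stop before about week 48 (156.5 − 108.4 = 48.1) would be censored before it.
- Alternatively, keep 4 years and extend scheduled progression follow-up explicitly past 4 years from treatment start.

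**Cost.** The first three changes need no new visits, and Section 12.1.2 already provides a follow-up form. They do need an amendment with IRB approval under Section 13.1, which should disclose that a prespecified landmark was dropped after accrual was reported. The time-to-event readout would come about 108 weeks (4 + 104.4) after the response readout. Keeping 4 years would add roughly 20 to 24 weeks of follow-up for completers, and about 76 weeks for a patient who stops at week 24.
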